9.4 Subgroup analyses: N/A

9.5 Adjusted analysis: N/A

9.6 Interim analysis and criteria for the premature termination of the trial: N/A

9.7 Participant population

All participants will be included in the analysis in an intention to treat analysis and participants who have completed the study will be included in a completer analysis.

9.8 Procedure(s) to account for missing or spurious data

Any missing data will be imputed in a last observation carried forward model.

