2.7 Table of endpoints/outcomes

Objectives	Outcome Measures	Timepoint of evaluation of this outcome measure
Primary Objective To assess the efficacy of tDCS treatment.	Clinical response as measured by MADRS score improvement of >= 50% following the course of tDCS treatment	End of tDCS sessions (visit 21)
Secondary Objectives To assess the acceptability and safety of the intervention	Participant retention at the end of the treatment who have completed a minimum of 15 tDCS sessions Participant acceptability questionnaire scales tDCS Adverse Events Questionnaire	End of tDCS sessions (visit 21) At each session

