6.2 Consent

The Chief Investigator (PI) retains overall responsibility for the conduct of research which includes the taking of informed consent of participants at their site. The PI will ensure that any person delegated responsibility to participate in the informed consent process is duly authorised, trained and competent to participate according to the ethically approved protocol, principles of Good Clinical Practice (GCP) and Declaration of Helsinki.

Informed consent will be obtained prior to the participant undergoing procedures that are specifically for the purposes of the trial and are out-with standard routine care at the participating site.

The right of a participant to refuse participation without giving reasons will be respected.

The participant will remain free to withdraw at any time from the trial without giving reasons and without prejudicing his/her further treatment and will be provided with a contact point where he/she may obtain further information about the trial. Data and samples collected up to the point of withdrawal will only be used after withdrawal if the participant has consented for this. Any intention to utilise such data is outlined in the consent literature. Where a participant is required to re-consent or new information is required to be provided to a participant, the PI will ensure this is done in a timely manner.

The PI takes responsibility for ensuring that all vulnerable participants are protected and participate voluntarily in an environment free from coercion or undue influence.

The potential participant will discuss with an individual knowledgeable about the research about the nature and objectives of the trial and possible risks associated with their participation. The potential participant will have the opportunity to ask questions.

The written material (information leaflet and consent document) is approved by the REC and is in compliance with GCP, local regulatory requirements and legal requirements

All participants will be capable of giving consent for themselves:

- understand the purpose and nature of the research
- understand what the research involves, its benefits (or lack of benefits), risks and burdens
- understand the alternatives to taking part
- be able to retain the information long enough to make an effective decision.
- be able to make a free choice
- be capable of making this particular decision at the time it needs to be made

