6.10 Withdrawal criteria

Participants will be withdrawn from the trial if they do not comply with the intervention, namely if they are unable to have a minimum of 50% of the tDCS session (10 out of 21 sessions), or if they develop serious adverse effects from any part of the study. Recording of the reasons for withdrawal will be made. Should a participant lose capacity to consent during the study then they would be withdrawn from the study, and that their identifiable data already collected with consent would be retained for use, and that no further data collection would take place. Their GP will be informed about their withdrawal, and there will have a telephone follow up at 1 month following their withdrawal.

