9.3.2 Primary outcome analysis

The primary outcome analysis clinical response which will be measured by the number of enrolled participants who show a clinical response at the end of treatment (MADRS score improvement of $\geq 50\%$ following the course of tDCS treatment), divided by the total number of enrolled participants, expressed as a percentage.

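### Carrying the last observation forward for all missing data turns a mid-course MADRS response into an end-of-treatment response and fills the end-of-course acceptability rating from baseline

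*Combined protocol and SAP*

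**What the plan says.** Section 9.8 is one sentence: "Any missing data will be imputed in a last observation carried forward model". It makes no distinction by endpoint, visit or reason for missingness. Section 9.7 adds "All participants will be included in the analysis in an intention to treat analysis" and, alongside it, that "participants who have completed the study will be included in a completer analysis".

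The primary analysis in 9.3.2 takes the "number of enrolled participants who show a clinical response at the end of treatment" and divides by everyone enrolled. Section 2.7 times the endpoint at visit 21.

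The schedule of events (section 11) shows one MADRS between the first treatment visit and the end of the course. Acceptability is defined in 9.3.3 as the percentage giving a rating of 5 to 7 after the six-week course. The questionnaire is listed as baseline data in 6.6 and is completed at the final session under 6.9. The schedule shows no mid-course acceptability rating.

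Two further provisions bear on what can be carried forward. Section 6.2 says: "Data and samples collected up to the point of withdrawal will only be used after withdrawal if the participant has consented for this". Section 6.10 withdraws participants who receive too few sessions, or "if they develop serious adverse effects from any part of the study".

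**The concern.** For the primary endpoint, LOCF replaces a missing visit 21 outcome with whatever was last recorded. Someone who had reached 50% improvement at mid-course and then left is reported as an end-of-treatment responder, even if withdrawn for serious adverse effects. That is not the endpoint in 2.7 and 9.3.2, and no section says which rule prevails. Section 9.8 also gives no rule where nothing may be carried forward, as when a participant has not consented to use of data from before withdrawal.

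For acceptability, the only value available to carry is the baseline one, so a secondary endpoint about the completed course would include answers from people who never rated it.

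There is no control arm in which a similar error could offset this one. Section 1 says the results will inform the design of a sham-controlled trial, so an inflated response rate would pass into that design.

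**Working it through.** **Inputs.** 50 enrolled, 10% attrition, 45 completers (9.1): 50 × 0.90 = 45, so 5 expected non-completers. Pilot discontinuation was 2 of 26 (1.1): 2/26 = 7.7% (printed as 7.6%), and 0.077 × 50 = 3.8, about 4 of 50. By column count the mid-course MADRS falls at about day 15, with the last session at day 39; the table is broken in extraction, so this is approximate.

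**Assumptions.** All non-completers lack a final MADRS (9.1 speaks of completing the course, not of missing ratings; fewer missing ratings would scale the effect down). Among those who leave after the mid-course rating, 20% to 40% had already responded; the documents give no such figure.

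**Primary endpoint.** The comparator is a missing final MADRS counted as non-response.

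Gain from LOCF = non-completers × share leaving after the mid-course rating × share of those already responding ÷ 50. Each carried response adds 1/50 = 2 points.

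| Scenario | Calculation | Gain (points) |
|---|---|---|
| 5 leave, all before mid-course | 5 × 0 / 50 | 0 |
| 5 leave, half after | 5 × 0.5 × 0.2 / 50 to 5 × 0.5 × 0.4 / 50 | 1 to 2 |
| 5 leave, all after | 5 × 0.2 / 50 to 5 × 0.4 / 50 | 2 to 4 |
| 5 leave, all after, all responding | 5 / 50 | 10 (unlikely ceiling) |
| 4 leave (pilot rate), all after | 4 × 0.2 / 50 to 4 × 0.4 / 50 | 1.6 to 3.2 |
| 4 leave, all after, all responding | 4 / 50 | 8 (ceiling) |

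The zero case is realistic for some of those withdrawn under 6.10 for too few sessions.

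**Illustration**, assuming 22 of 45 completers respond (exact Clopper-Pearson 95% intervals):

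- Missing counted as non-response: 22/50 = 44.0% (30.0% to 58.7%, width 28.7 points).
- LOCF, all five leaving after mid-course: (22 + 1)/50 = 46.0% to (22 + 2)/50 = 48.0%.
- Completers: 22/45 = 48.9% (33.7% to 64.2%).

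**No usable data under 6.2.** If such participants were dropped from the denominator, the rate would run from 22/49 = 44.9% (30.7% to 59.8%) for one person to 22/45 = 48.9% for all five, against 44.0% over all enrolled.

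**Acceptability**, assuming 36 of 45 rate 5 to 7: 36/45 = 80% of those rated and 36/50 = 72% of all enrolled. With five baseline answers carried forward, the result lies anywhere from 36/50 = 72% to 41/50 = 82%, decided entirely by those five answers. The item in 9.3.3 asks, in the past tense, about sessions received. The documents do not give the wording of the baseline form. If it is the same item, the course it asks about has not been received; if it is a different item (healthy controls also complete a baseline form, 2.6), the answers are not comparable.

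**YMRS (minor, exploratory).** Entry requires a score of 8 or less (5.1.2) and the outcome is a score above 13 (2.6). A carried-forward entry-level score can never reach the threshold. This affects only participants with no post-baseline YMRS, and mania would still be recorded as an adverse event.

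**The case against.** The strongest reply is that 9.3.2 already answers the question: a person with no end-of-treatment rating does not show a response then, and remains in the denominator. That reading is available, but it conflicts with the unqualified rule in 9.8 and nothing sets precedence. Two analysts following the plan could report different primary results.

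Second, the upward direction follows from the comparator. Missing counted as non-response is the lowest possible rate, so any imputation equals or exceeds it. This stands: LOCF is not shown to exceed the true end-of-treatment rate, and someone only partly improved at mid-course might have responded later. The point is narrower: the plan reports a mid-course state as an end-of-treatment one and offers no conservative figure beside it.

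Third, the effect is small and rests on assumptions. Stopping stimulation does not by itself mean a missing MADRS, and withdrawal for serious adverse effects should be rare, since 1.1 cites none in over 33,200 sessions. This also stands and limits the severity.

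Fourth, 6.2 refers to consent material that is not in the document, so the number with unusable data cannot be judged, and dropping them would contradict the denominator in 9.3.2. Both are true, but 9.8 still gives no rule for them.

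Fifth, 9.3.3 names all enrolled as the denominator for retention but not for acceptability, which may imply observed ratings only, and the baseline form might have been completed at the first session visit. Neither removes the fault: 9.8 exempts nothing, and a first-session answer is still not a rating of the completed course.

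**Conclusion.** The concern holds. As written, 9.8 conflicts with the timing of the primary endpoint and yields an invalid acceptability value for anyone without a final rating.

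At the planned attrition, with every non-completer lacking a final MADRS, the response rate rises over the non-response rule by 0 to 4 points in the plausible scenarios, with 10 as a ceiling. Only the reported estimate is affected, since there is no test or success threshold. The completer analysis leaves these participants out, so with 9.8 applied neither planned analysis supplies the conservative rate. The acceptability fault does not depend on any assumed response rate, although its size does depend on how many final ratings are missing. The YMRS point is minor. This should be fixed before analysis.

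**What to change.** 1. In 9.3.2 and 9.8, state that an enrolled participant with bipolar depression who has no end-of-treatment MADRS counts as a non-responder and non-remitter in the primary analysis, including anyone whose earlier data may not be used under 6.2. Keep LOCF and completer analyses as sensitivity analyses, and report how many participants lack a final MADRS.
2. Exclude acceptability from LOCF. Report the number rating 5 to 7 over those rated at the end of the course, with the same count over all enrolled beside it.
3. Do not carry a baseline YMRS forward; report the number with a post-baseline YMRS.

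The cost is a few sentences of SAP wording, with no new visits or data. The reported response percentage may be a few points lower, and the non-response rule may understate the effect for people whose rating is missing for unrelated reasons. The sensitivity analyses would show by how much.

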11 SCHEDULE OF EVENTS

Study Procedure	Screening	Treatment Period																				Follow up	
		V0	V1	V2	V3	V4	V5	V6	V7	V8	V9	V10	V11	V12	V13	V14	V15	V16	V17	V18	V19	V20	
Visit	V0	C/H	C/H	C/H	C/H	C/H	C/H	C/H	C/H	C/H	C/H	C/H	C/H	C/H	C/H	C/H	C/H	C/H	C/H	C/H	C/H	C/H/T	
Location		C/H	C/H	C/H	C/H	C/H	C/H	C/H	C/H	C/H	C/H	C/H	C/H	C/H	C/H	C/H	C/H	C/H	C/H	C/H	C/H	C/H	
Week of Treatment	Wk -4 to 0	Wk1	Wk1	Wk1	Wk1	Wk1	Wk2	Wk2	Wk2	Wk2	Wk2	Wk3	Wk3	Wk3	Wk3	Wk4	Wk4	Wk5	Wk5	Wk6	Wk6	Wk18	
Day of Visit	-20	1	2	3	4	5	8	9	10	11	12	15	16	17	18	19	22	25	29	32	36	39	126
Visit Window (days)	± 3	± 3	± 3	± 3	± 3	± 3	± 3	± 3	± 3	± 3	± 3	± 3	± 3	± 3	± 3	± 3	± 3	± 3	± 3	± 3	± 3	± 3	± 14
Screen Information & Consent	x																						
Study Information Sheet		x																					
Inclusion/Exclusion Criteria	x	x																					
Clinical Assessments																							
Demographics	x																						
Height	x																						
Weight	x																						
Clinical Interview	x																						
Pre-existing conditions	x																						
History or treatments	x																						
Concomitant treatments	x	x	x	x	x	x	x	x	x	x	x	x	x	x	x	x	x	x	x	x	x	x	
tDCS training session		x																					
tDCS intervention	x	x	x	x	x	x	x	x	x	x	x	x	x	x	x	x	x	x	x	x	x	x	
Rating Scales																							
MINI	x																						
IQ assessment		x																					
MADRS	x	x										x									x	x	
PHQ-9		x										x									x	x	
HAMA		x										x									x	x	
YMRS		x										x									x	x	
SDS		x										x									x	x	
Q-LES-Q		x										x									x	x	
tDCS Adverse Events Scale	x	x	x	x	x	x	x	x	x	x	x	x	x	x	x	x	x	x	x	x	x	x	
Acceptability questionnaire	x																			x	x		
EEG	x																			x			
Neuropsychological tasks (eg. SDMT, RAVLT,)		x																			x		

Location: Clinic (C), Home (H), Telephone (T)
